### **6.3. RESPONSE EVALUABLE SET [RES]**

The RES is defined as all patients who received at least 1 dose of HMPL-523, have a baseline tumor measurement, and have at least 1 post-baseline tumor measurement or clinical restaging, unless death occurs before the first post-baseline assessment. The RES will be the primary population for the analysis of ORR, TTR, and DoR.

HMPL-523

---

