5 MATERIALS AND METHODS

5.1 Patients

5.1.1 Inclusion Criteria

Patients must meet the following criteria to be eligible for study entry:

1. Signed informed consent form (ICF).
2. Age \geq 18 years.
3. ECOG performance status of 0 or 1.
4. Histologically confirmed lymphoma, including HL and NHL.

In the dose expansion stage, the tumor types may be restricted to any or all of the following tumor types. There may be approximately 10 patients in each cohort depending on response signals suggesting efficacy, except for HL cohort with 25 patients and 2 identified cohorts with approximately 20 patients per cohort: relapsed or refractory CLL/SLL (n = 10), and CLL/SLL post-BTK exposure (n = 20), MCL, FL (Grade 1-3a) (n = 20), MZL, WM/LPL, PTCL, and CBCL. As of Amendment 5, the study was closed to new enrollment.

5. Patients with relapsed or refractory lymphoma who have exhausted all approved therapy options as defined below:
 - a. Refractory to any prior regimen, defined as no response (CR or PR) to previous therapies, or progression within 6 months of completion of the last dose of prior therapy.
 - b. Those who can no longer tolerate/withstand cytotoxic chemotherapy and/or available standard of treatment/care. Where safety profile and risks of toxicity of other treatment options far outweigh any possible clinical benefit.
 - c. Those with no curative standard of treatment or where available treatments are not reasonable or do not make sense. In particular, in the opinion of the attending primary investigator, those who will benefit from a new class of compound with a different mechanism of action.
 - d. Patients enrolled in the post-BTK CLL cohort should have either disease progression or intolerance to prior BTK inhibitor therapy to enroll. Approximately 10 out of the 20 patients in this cohort should also have disease progression or intolerance to prior BCL-2 (venetoclax or BCL-2 inhibitor on clinical trial) exposure.
6. In the dose expansion stage, patients must have measurable disease for an objective response assessment, except for patients with CLL and WM/LPL.

NOTE: Measurable disease with FL, MCL, MZL, PTCL, CBCL, HL, or SLL is defined as at least 1 bi-dimensionally measurable lesion (nodal disease $>$ 1.5 cm, non-nodal disease $>$ 1 cm in its longest dimension by computed tomography [CT] scan), as defined in [Appendix 6](#).

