5.6.12 Tumor and Response Evaluation

All evaluable lesions should be assessed and documented at screening and re-assessed at each subsequent tumor evaluation, using blood test, physical examination, and contrast-enhanced CT scans (neck, chest, abdomen, and pelvis) for indolent NHL and/or positron emission tomography (PET)-CT for HL and aggressive NHL. Enhanced magnetic resonance imaging (MRI) may be used instead of enhanced CT scans in patients for whom CT scans are contraindicated.

Tumor assessment will be conducted every 8 weeks (± 7 days) for the first 24 weeks and every 12 weeks (± 7 days) thereafter until the patient has the first progression, starts new anticancer therapy, or dies. Patients who discontinue study drug due to reasons other than disease progression will remain on the study and will be followed quarterly for tumor assessment until the patient has their first progression, starts new anticancer therapy, or dies or until 12 months after their initial dose of the study drug. Tumor assessment will also be conducted at study completion or early termination (for reasons other than disease progression).

The same imaging procedure and laboratory tests used to define evaluable lesions at baseline should be used throughout the study for each patient.

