7.2 Analysis Population

The following analysis populations are defined for the study:

Full Analysis Set (FAS):

The FAS is defined as all patients who receive at least 1 dose of HMPL-523. The FAS will be used for analysis of safety data and efficacy data.

DLT Evaluable Analysis Set:

The DLT Evaluable Analysis Set is defined as all patients enrolled in the dose escalation phase of the study who are evaluable for DLT assessment. A subject is DLT evaluable if he/she meets the following criteria:

- has received at least 75% of the assigned dose of study medication during the DLT assessment window

OR

- has not completed the DLT assessment period due to a DLT

Response Evaluable Set (RES):

The RES is defined as all patients who receive at least 1 dose of HMPL-523, have either a baseline tumor measurement for patients with non-WM/LPL or baseline quantitative serum immunoglobulin assessment for patients with WM/LPL, and have at least 1 post-baseline tumor measurement or clinical restaging. The RES will be the primary population for the analysis of ORR, TTR, and DoR.

Pharmacokinetics Analysis Set (PKAS):

The PKAS is defined as all patients who received at least 1 dose of HMPL-523 and have at least 1 PK sample obtained and analyzed.

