## 2. INTRODUCTION

This study is a two-stage, open-label, multicenter Phase 1 study to evaluate the safety, Pharmacokinetics (PK), and preliminary efficacy of HMPL-523 in patients with relapsed or refractory lymphoma who have exhausted approved therapy options. The study consists of two stages. Stage 1 is a dose escalation phase, in which a modified 3+3 design is applied for the dose escalation and to determinate the maximum tolerated dose (MTD) / recommended Phase II dose (RP2D). Stage 2 is a dose expansion stage, in which the safety, tolerability, PK, and preliminary efficacy of HMPL-523 at MTD/RP2D will be further evaluated in patients with relapsed, refractory, or resistant NHL.

The purpose of this Statistical Analysis Plan (SAP) is to provide a description of the statistical methods and conventions to be implemented in the presentation and analysis of efficacy and safety data from study 2018-523-00US1. This document is based on Protocol Amendment 5 dated 14Jun2024. It describes the data to be summarized and analyzed, including specifics of the statistical analyses to be performed. If circumstances arise during the study such that more appropriate analytic procedures become available, the SAP may be revised. This SAP supersedes the statistical considerations identified in the protocol; where considerations are substantially different, they will be identified. Any revisions to the SAP will be made and finalized prior to the final Database Lock (DBL), and any deviations from the SAP will be documented in the final Clinical Study Report (CSR).

The PK and pharmacodynamics analyses will be described in a separate analysis plan. All statistical analyses except for PK specific analyses will be performed by IQVIA Biostatistics.

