## 16. EFFICACY OUTCOMES

Tumor assessment will be conducted every 8 weeks ( $\pm$  7 days) for the first 24 weeks and then every 12 weeks ( $\pm$  7 days) thereafter.

Efficacy analysis will be performed using the RES for ORR, TTR, and DoR endpoints and using the FAS for the PFS endpoint.

Unless otherwise specified, all efficacy outputs are to be summarized by dose cohort for Stage 1 and by type of malignancy in Stage 2.

HMPL-523

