### **Progression free survival (PFS)**

PFS is defined as the time (in months) from the date of first study medication to the earliest date of disease progression or death due to any reason whichever occurs first.

HMPL-523

PFS (months) = ([date of progression or death or censoring] - [date of first dose of study medication] + 1)/30.4375.

A patient is deemed to be censored according to the rules specified in **Error! Reference source not found.** below.

Error! Reference source not found.: **Progression-Free Survival Censoring Rules**

#	Situation	Date of Progression or Censoring	Outcome	Event/Censor reason
1	Death (without previously documented progressive disease [PD]) within two evaluable tumor assessments [a] from last evaluable tumor assessment or first dose (if no post-baseline tumor assessment)	Date of death	Event	Death
2	Death (without previously documented PD) after two or more consecutive missed/non-evaluable tumor assessments [a] from last evaluable tumor assessment or first dose (if no post-baseline tumor assessment)	Date of last evaluable tumor assessment or date of first dose (if no post-baseline tumor assessment)	Censored	Death after two or more consecutive missed or NE tumor assessments
3	Progression within two evaluable tumor assessments [a] from last evaluable tumor assessment or first dose (if no post-baseline tumor assessment before PD)	Date of progression	Event	Disease Progression
4	Progression after two or more consecutive missed/non-evaluable tumor assessments [a] from last evaluable tumor assessment or first dose (if no post-baseline tumor assessment before PD)	Date of last evaluable tumor assessment or date of first dose (if no post-baseline tumor assessment before PD)	Censored	Progression after two or more consecutive missed or NE tumor assessments
5	Progression after new anti-cancer treatment	Date of last evaluable tumor assessment before new anti-cancer treatment or date of first dose (if no post-baseline tumor assessment before new anti-cancer)	Censored	Progression after new anti-cancer therapy
6	No baseline tumor evaluable assessment and alive	Date of first dose	Censored	No baseline assessment
7	No post-baseline tumor evaluable assessment and alive	Date of first dose	Censored	No post-baseline assessment

HMPL-523

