-  The baseline tumor assessment can be completed within 21 days prior to enrolment. All measurable and evaluable lesions should be assessed and documented at this visit, using blood, physical examination and CT scan (neck, chest, abdomen, pelvis, liver/spleen) every 8 weeks (+/-7 days) for the first 24 weeks and then every 12 (+/-7 days) weeks thereafter. At study termination or early termination (other than disease progression) of the patients, tumor assessment will be also conducted. The same imaging procedure and laboratory tests used to define measurable lesions at baseline should be used throughout the study for each patient.
-  Blood samples should be collected according to the time-points tables in [Appendix 2](#) and [Appendix 3](#) of protocol Amendment 5. At the sponsor's discretion, some patients in the expansion stage may be required to provide samples for pharmacodynamics analysis. This will be based on certain signals as determined by the study team. The time points for these pharmacodynamic samples will be determined at the time of patient selection.
-  After informed consent, but prior to initiation of study medications, only SAEs caused by a protocol-mandated intervention will be collected (eg, SAEs related to invasive procedures such as biopsies, medication washout, or no treatment run-in). After initiation of HMPL-523 treatment, all AEs and SAEs regardless of attribution will be collected until 30 days following the last administration of study treatment or study discontinuation/termination, whichever is later. After this period, investigators should report only SAEs that are related to prior HMPL-523 treatment.
-  Preferably within 7 days prior to the first dose of the study drug.
-  Fresh or archival tumor tissue consisting of a cell block or 10 unstained slides should be collected for patients in dose expansion cohorts during screening.

HMPL-523

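### SAP 6.3 asks every patient in the Response Evaluable Set for a baseline tumor measurement, although expansion-stage CLL and WM/LPL patients may enter without measurable disease

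*SAP*

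**What the plan says.** **Eligibility.** Protocol 5.1.1, Inclusion Criterion 6, states that in the expansion stage "patients must have measurable disease for an objective response assessment, except for patients with CLL and WM/LPL". SLL is among the types that must have a measurable lesion.

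**Analysis set, protocol.** Protocol 7.2 defines the RES as treated patients who "have either a baseline tumor measurement for patients with non-WM/LPL or baseline quantitative serum immunoglobulin assessment for patients with WM/LPL" and who have a later tumor measurement or clinical restaging. WM/LPL has its own route. CLL falls in the tumor-measurement branch.

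**Analysis set, SAP.** SAP 6.3 requires that patients "have a baseline tumor measurement, and have at least 1 post-baseline tumor measurement or clinical restaging", with an allowance for death before the first post-baseline assessment. There is no disease-specific route for anyone. Clinical restaging is accepted after baseline but not at baseline.

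**Precedence.** SAP Section 2: "This SAP supersedes the statistical considerations identified in the protocol".

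**Use.** SAP Section 16: "Efficacy analysis will be performed using the RES for ORR, TTR, and DoR endpoints and using the FAS for the PFS endpoint". Row 6 of the PFS censoring table (SAP 16.1.1) covers the case "No baseline tumor evaluable assessment and alive" and censors at first dose.

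**The concern.** Two disease types are exempt from measurable disease at entry because their response is not judged by lesion size alone. The set used for the response endpoints then asks for a tumor measurement at baseline. Of the two exempt types, the protocol accommodates one and the SAP accommodates neither. The loss of the WM/LPL route is a direct mismatch between the documents. SAP 6.3 gives no reason for it; the SAP's modification history is blacked out, so a reason may stand there.

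Preliminary efficacy in the expansion stage is a primary objective, and protocol 2.2.4.5 gives the efficacy rationale for the larger post-BTK CLL cohort. These cohorts are very small, so removing one or two patients on a ground unrelated to whether they can be assessed may move the estimate substantially. The study is open-label, so if the wording is left to interpretation during programming, the choice may be made by people who already know the responses.

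**Working it through.** **1. Expansion total.** Protocol Table 2, Amendment 5 column: 25 + 1 + 7 + 2 + 2 + 1 + 1 + 9 + 0 = 48. This reproduces the stated enrollment of 48.

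**2. Upper bound on patients exposed.**
- CLL: 1 + 7 = 8, and 8/48 = 16.7%.
- Adding WM/LPL: 8 + 1 = 9, and 9/48 = 18.8%.

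The number without a measured baseline lesion is not in the documents. Call it k among the 8 CLL patients, with k anywhere from 0 to 8. The eligibility text describes these cohorts as CLL/SLL, and any SLL patient must have a measurable lesion, which lowers the bound. Stage 1 patients are not counted, because Inclusion Criterion 6 applies only in expansion and Stage 1 counts by disease are not given.

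**3. The rules side by side.**

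| | CLL | WM/LPL | Other types |
|---|---|---|---|
| Measurable disease needed in expansion (Inclusion 6) | No | No | Yes |
| Baseline condition, protocol 7.2 | Tumor measurement | Serum immunoglobulin | Tumor measurement |
| Baseline condition, SAP 6.3 | Tumor measurement | Tumor measurement | Tumor measurement |
| Response possible without a measured lesion | Yes (Appendix 4) | Yes (Appendix 5) | Not relevant |

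**4. Why the last row reads yes.** Under Appendix 4, PR in CLL needs three things: a fall of at least 50% in lymphocyte count; a reduction of at least 50% in nodes, or liver enlargement, or spleen enlargement; and one blood-count criterion. A patient with lymphocytosis and an enlarged spleen can meet all three with no measured node. In Appendix 5, PR and minor response are graded by percentage fall in serum IgM, with extramedullary disease counted only if present at baseline.

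**5. Sensitivity, illustration only.** Assume 4 responders among the 8 CLL patients, all otherwise in the RES and summarized together. The denominator becomes 8 − k. The lowest ORR arises if those excluded were responders, the highest if they were non-responders. Intervals are 95% Clopper-Pearson, the plan's method.

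| k | Lowest ORR | Highest ORR |
|---|---|---|
| 0 | 4/8 = 50.0% (15.7 to 84.3) | the same |
| 1 | 3/7 = 42.9% (9.9 to 81.6) | 4/7 = 57.1% (18.4 to 90.1) |
| 2 | 2/6 = 33.3% (4.3 to 77.7) | 4/6 = 66.7% (22.3 to 95.7) |
| 4 | 0/4 = 0% (0 to 60.2) | 4/4 = 100% (39.8 to 100) |

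For WM/LPL, excluding the single expansion patient leaves 1 − 1 = 0, so there would be no ORR estimate for that type.

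**The case against.** **The term is undefined.** SAP 6.3 says tumor measurement, not measurable disease. CT is scheduled at screening, and Appendix 4 judges spleen and liver reduction by CT. A CT spleen size, or a node below the size cutoff, could be read as a baseline tumor measurement, and then few or no CLL patients would be lost. This stands as a possible reading, and it is why the exclusion is described as literal and not certain. The documents lean the other way. Protocol 7.2 needed a separate route for WM/LPL, which suggests that the term was not meant to cover non-lesion assessments. The SAP builds tumor burden from the diameters of target lesions and lists spleen and liver assessment under its own heading (17.8). The CT reading also does nothing for a WM/LPL patient followed by IgM alone.

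**The group that can change the numerator is narrow.** PR in CLL requires a node, liver or spleen reduction, so a patient assessable only by blood or marrow cannot reach it. This stands. The lower ends of the ranges above assume excluded responders with a spleen or liver route, or a complete or nodular partial response. Non-responders still belong in the denominator.

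**The consequence is limited.** This is a closed, single-arm Phase I study with descriptive estimates. Protocol 7.3.5 lists best response for all patients, and SAP 9.1 lists set membership by patient, so an exclusion would be visible. This also stands, but the tabulated ORR would still rest on the reduced set.

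**A stronger reading that the documents do not support.** A reader might infer that row 6 of the PFS table also requires a tumor measurement, and so censors living CLL patients on Day 1 (PFS of 1/30.4375 = 0.033 months) while deaths count as events. Row 6 refers to an evaluable assessment, not a measurement, and PFS is analyzed in the FAS. Protocol 5.6.12 describes tumor evaluation as "using blood test, physical examination, and contrast-enhanced CT scans (neck, chest, abdomen, and pelvis) for indolent NHL", with PET-CT for other types, and SAP Appendix 1, footnote 21, says "All measurable and evaluable lesions should be assessed and documented at this visit, using blood, physical examination and CT scan". A CLL patient with screening counts, examination and CT has such an assessment, so Day 1 censoring does not follow. Two loose ends remain: evaluable is not defined for CLL, and a living patient without an evaluable baseline who later progresses could match both row 3 and row 6, with no order of precedence stated.

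**Conclusion.** The conflict between Inclusion Criterion 6 and SAP 6.3 is in the text, and the SAP has lost the WM/LPL route that the protocol provides. Read literally, the RES rule removes eligible CLL and WM/LPL patients who can be assessed for response from ORR, TTR and DoR. The exposure is at most 9 of 48 expansion patients, fewer if any in the CLL cohorts have SLL, and possibly none among the CLL patients if all had a measured baseline lesion. The size of any effect on ORR is unknown; the table in step 5 rests on an assumed responder count and assumed values of k, and shows sensitivity, not bias that has occurred. No PFS bias is established. The point merits a change because it fixes the denominator of a primary-objective endpoint in very small cohorts.

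**What to change.** In SAP 6.3, define evaluability by disease, at baseline and after baseline:
- **CLL:** a disease assessment under Appendix 4, meaning lymphocyte count with node, liver and spleen assessment.
- **WM/LPL:** quantitative serum immunoglobulin, as in protocol 7.2.
- **Other types:** a tumor measurement.

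As a clarification only, state in SAP 16.1.1 that evaluable in the PFS censoring table, row 6 included, means evaluable under the criteria for that disease.

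The cost is SAP wording and the matching derivation of the RES flag, before the final database lock. No new data are needed: hematology, examination of nodes, liver and spleen, CT, and serum immunoglobulin for WM/LPL are already scheduled at screening and during treatment.

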#### **6.4. DLT EVALUABLE ANALYSIS SET (DEAS)**

The DLT Evaluable Analysis Set (DEAS) is defined as all patients who have received at least 75% of the assigned dose of study treatment during the DLT assessment window of 28 days (ie, from Cycle 1, Day 1 [the day of the first administration of treatment] through Cycle 1, Day 28) in Stage 1 or have not completed the DLT assessment period due to a DLT.

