4.4 Definition of a Dose-Limiting Toxicity

DLTs are defined as the occurrence in the DLT assessment window (see Section 4.4.1) of any of the following TEAEs, unless they are clearly unrelated to the study drug:

- a. Nonhematologic toxicity: All nonhematologic TEAEs of Grade 3 or greater with the exception of:
 - i. Grade 3 nausea, vomiting controlled by supportive therapy
- b. Hematologic toxicity:
 - i. Grade 4 neutropenia lasting more than 5 days.
 - ii. Grade 4 thrombocytopenia or Grade 3 thrombocytopenia with bleeding or any requirement for platelets transfusion.
 - iii. Grade 3 or greater febrile neutropenia (defined as ANC < 1000/mm³ with a single temperature of > 38.3°C (101°F) or a sustained temperature of ≥ 38°C (100.4°F) for more than 1 hour.
 - iv. Grade 4 anemia unexplained by underlying disease.

- c. Any TEAE requiring a dose delay of ≥ 15 days.
- d. Any case of Hy's Law.

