4.4.2 Definition of Dose-Limiting Toxicity Evaluable Patient

For decisions on dose escalation, each dose cohort shall present protocol-required number of DLT evaluable patients. A patient is DLT evaluable if he/she meets the following criteria:

- Has received at least 75% of the assigned dose of study medication during the DLT assessment window

OR

- Has not completed DLT assessment period due to a DLT

Patients who are not DLT evaluable in a dose cohort will be replaced to guarantee the protocol required number of DLT evaluable patients for dose escalation evaluations.

4.4.3 Dosing Beyond Cycle 1

Patients who complete the DLT assessment window (Cycle 1 Days 1-28) and are deemed by the investigator to be benefiting from treatment with HMPL-523 may continue treatment with HMPL-523 until disease progression, intolerable toxicity, at investigator's assessment that the patient is no longer benefiting from the study treatment, patient withdrawal from the study, the end of the study, or death. Conversely, if in the opinion of the attending principal investigator the patient may have clinical benefit from a higher dose, then, at the request of the principal investigator and with the approval of the sponsor, the patient may be able to participate in inpatient dose escalation (Section 4.3). If the study is terminated or ends before a patient reaches any of these endpoints, refer to Section 5.3.5.

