4.4.4 Definition of Maximum Tolerated Dose

The MTD is defined as the maximum dose at which no more than 16.7% patients in a single cohort experiences a DLT in the first cycle (Cycle 1 Days 1-28).

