5.4 Dose Delays and Modification

5.4.1 During Dose-Limiting Toxicity Assessment Window

If a patient experiences a TEAE of Grade 3 or Grade 4 and/or unacceptable toxicity including a DLT not attributable to the disease or disease-related processes under investigation, dosing will be interrupted and supportive therapy will be administered as required in accordance with local practices/guidelines.

Patients who experience a DLT may resume dosing at the same or the previous lower dose level at the discretion of the investigator if the toxicity is resolved or improved to baseline level. If a patient experiences an unacceptable toxicity at the reduced dose level, he/she will be discontinued from treatment. No patient will have his/her dose reduced by more than 2 dose levels. Once dose is reduced, it cannot be re-escalated.

If a clinically significant TEAE or unacceptable toxicity that does not meet the definition of a DLT is observed, the patient may receive subsequent doses to complete the dosing schedule, provided that the TEAE is improved to CTCAE Grade ≤ 2 within 2 weeks.

Dose reduction in patients without DLT is not permitted in the DLT assessment window without the sponsor's approval.

5.4.2 After Dose-Limiting Toxicity Assessment Window in Stage 1 or in Stage 2

After the DLT assessment window in Stage 1 or in Stage 2, the dose of HMPL-523 may be interrupted and/or reduced to the next lower dose level (600 mg) if any of the following are observed:

- Grade 3 or 4 hematologic toxicity
- Grade 3 or 4 nonhematologic toxicity (except for alopecia and skin eruption, nausea, vomiting, diarrhea, or constipation if well-controlled by systemic or topical medication)

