## **17. SAFETY OUTCOMES**

All outputs for safety outcomes will be based on the FAS with the exception of DLT which will be based on DLT evaluable analysis set.

HMPL-523

---

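### As worded, SAP 6.4 leaves out of the DLT Evaluable Analysis Set a Stage 1 patient who has a DLT, resumes dosing and reaches Day 28 on under 75% of the assigned dose

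*SAP*

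**What the plan says.** SAP 6.4 defines the DEAS by two alternatives. The first covers "all patients who have received at least 75% of the assigned dose of study treatment during the DLT assessment window of 28 days". The second covers Stage 1 patients who "have not completed the DLT assessment period due to a DLT". Protocol 4.4.2 uses the same pair for escalation decisions, with the second alternative worded "Has not completed DLT assessment period due to a DLT", and Protocol 7.2 repeats it. Neither document says that a patient with a DLT is evaluable whatever dose was received.

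Four other provisions bear on this:

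- **Resumption.** Protocol 5.4.1 interrupts dosing for a DLT and then states: "Patients who experience a DLT may resume dosing at the same or the previous lower dose level at the discretion of the investigator". This is conditional on resolution or improvement to baseline.
- **A DLT defined by a dose gap.** Criterion (c) in Protocol 4.4 is "Any TEAE requiring a dose delay of" 15 days or more.
- **Replacement.** Protocol 4.4.2: "Patients who are not DLT evaluable in a dose cohort will be replaced".
- **Reporting.** SAP 17 puts all safety outputs on the Full Analysis Set (FAS), "with the exception of DLT which will be based on DLT evaluable analysis set". SAP 17.1 builds the Stage 1 DLT summary on the DEAS, including the number of patients with a DLT, and separately lists all DLTs by subject and dose level. Protocol 7.3.3 places the DLT summary on the FAS.

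The MTD in Protocol 4.4.4 is the highest dose at which "no more than 16.7% patients in a single cohort experiences a DLT in the first cycle".

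**The concern.** The 75% threshold exists to remove patients too lightly exposed to be informative about toxicity. A patient who has already had a DLT is informative at any exposure, and the second alternative is there to keep such patients. It does so only when the window was not completed. Protocol 4.4.1 defines the window as Days 1 to 28, and Protocol 4.2 speaks of patients completing it without a DLT, so completing the window and having a DLT are separate matters. A patient who has a DLT, is held, resumes and reaches Day 28 has completed the window. If the hold or a reduction brings the dose below 75%, that patient fails both conditions.

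DLT incidence is the primary safety outcome measure (Protocol 4.8.1). The gap acts only on patients who had a DLT, so whatever effect it has on the count is downward. The same wording also governs replacement and the six-patient escalation step, which counts evaluable patients.

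**Working it through.** **The plan's own figures.** The MTD limit is one patient in six: 1/6 = 16.7%. The Stage 1 sample-size figures follow from 1 − (1 − p)^6: 46.9%, 26.5% and 5.85% for p = 10%, 5% and 1%. The plan prints 5.8% for the last, which looks truncated.

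**Step 1: can the gap be reached at a constant dose?** With m missed days, the dose fraction is (28 − m)/28.

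- m = 7: 21/28 = 75.0%, still evaluable.
- m = 8: 20/28 = 71.4%, not evaluable by dose.
- m = 15, all inside the window: 13/28 = 46.4%.

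A 15-day hold must start by Day 13 for dosing to resume by Day 28. Starting on Day 13, doses are taken on Days 1 to 12 and Day 28, which is 13 in all. A hold starting on Day 22 leaves 21/28 = 75.0%, and the patient qualifies by dose. A hold starting on Days 15 to 21 leaves 14/28 to 20/28 (50.0% to 71.4%) and is still running on Day 28. Such a patient can reasonably be read as not having completed the window because of the DLT.

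**Step 2: resumption one level lower.** The SAP does not say whether assigned dose means the initial dose after a reduction. If it does, and the last full dose was on Day 7, fewer missed days are needed:

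| Change | Missed days | Fraction of initial dose |
|---|---|---|
| 700 to 600 mg | 5 | (7×700 + 16×600)/(28×700) = 74.0% |
| 800 to 600 mg | 3 | (7×800 + 18×600)/(28×800) = 73.2% |
| 600 to 400 mg | 1 | (7×600 + 20×400)/(28×600) = 72.6% |
| 400 to 200 mg | 0 | (7×400 + 21×200)/(28×400) = 62.5% |

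**Step 3: effect on one cohort.** Take six patients with two DLTs, one of them in the patient described.

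- All six counted: 2/6 = 33.3%. This is above 16.7%, and the six-patient rule halts escalation.
- That patient dropped and replaced by one without a DLT: 1/6 = 16.7%, which meets the limit.
- That patient dropped and not replaced: 1/5 = 20.0%.
- That patient and the replacement both counted: 2/7 = 28.6%, above the limit.

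The 1/6 result cannot arise if both DLTs fell in the initial three, because that rule counts patients enrolled and escalation stops there.

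**Step 4: effect on the expected rate.** Let q be the share of DLT patients who complete the window on under 75% dose. The documents do not give q, so a range is assumed. With true rate p, the rate among evaluable patients is p(1 − q)/(1 − pq). For p = 0.333:

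| q | Rate seen |
|---|---|
| 0 | 33.3% |
| 0.10 | 31.0% |
| 0.25 | 27.2% |
| 0.50 | 20.0% |

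At q = 0 nothing changes.

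**The case against.** A reader might infer that the DLT rate behind the MTD, and so the 700 mg RP2D, is understated. The documents do not support that.

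- They give no Stage 1 DLT counts and no Cycle 1 dose percentages, so they do not show that such a patient occurred.
- The MTD is worded on patients in a single cohort, and the initial-three rule counts patients enrolled. Only the six-patient step counts evaluable patients.
- Under Protocol 6.2.4, investigators report DLTs to the Safety Review Committee for each patient in the escalation stage, with no evaluability filter.
- Under Protocol 4.4.5 the RP2D rested on the MTD only if it was reached, and on PK with or without safety and efficacy findings. It is already set.

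A reader might also infer that the DEAS rule as a whole favours the drug. It does not: the 75% condition also removes under-dosed patients without a DLT, which raises the observed rate. Only the gap acts on DLT patients alone.

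The DLT would not vanish from the report either. Protocol 7.3.3.1 and SAP 17.1 list all DLTs, and the SAP table prints the number enrolled beside the number evaluable.

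All of this stands, and it limits the point to a conditional one about the summary. It does not remove the point. A listing does not correct a count in the summary of the primary safety measure, and the mixed denominators mean that the table and the MTD rule could disagree.

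**Conclusion.** The wording gap is real and can be reached under the protocol's own resumption rule. Its effect is conditional: if any Stage 1 patient had a DLT and completed Day 28 on under 75% of the assigned dose, the DEAS-based summary would undercount patients with a DLT. One such patient is enough to turn 33.3% into 16.7% in a cohort of six. That assumes a literal reading of window completion, a replacement without a DLT, and two DLTs not both in the initial three. If no such patient exists, no result changes. The number of such patients is unknown from the documents, and nothing here shows that the MTD or RP2D decision was wrong.

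**What to change.** Before database lock, which is when SAP 2 still allows revision:

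1. In SAP 6.4, define the DEAS as Stage 1 patients who experienced a DLT during the assessment window, regardless of dose received or window completion, or who received at least 75% of the assigned dose.
2. State whether assigned dose means the initial dose once a reduction has occurred.
3. Check every patient in the DLT listing against the DEAS flag and report any mismatch.
4. Reconcile SAP 17 (DLTs on the DEAS) with Protocol 7.3.3 (DLTs on the FAS) and with the cohort-based MTD wording in Protocol 4.4.4, and print the denominator used.
5. Rerun the Stage 1 DLT table on the revised set.

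No protocol amendment is needed. Escalation is complete and enrolment is closed, so changing Protocol 4.4.2 could not alter any escalation or replacement decision. The SAP states that it supersedes the protocol's statistical considerations. No clinical rule on holding or resuming treatment is touched.

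The cost is a short SAP edit, one cross-check and one table rerun on existing data. The downside is that a reported DLT rate could become slightly less favourable.
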